- Overall tumor response and tumor response in injected and uninjected lesions (Arm 1 only): The tumor response is evaluated up to the surgical resection. The overall tumor response is per the modified WHO ([Appendix D](#)). For tumor response in injected and uninjected lesions both subject-level and lesion-level response will be assessed. The subject-level injected and uninjected responses will be based on the tumor burden of only injected index lesions including injected new measurable lesions, or the tumor burden of only uninjected index lesions including uninjected new measurable lesions, respectively. The lesion-level response will evaluate the change of the area of each individual lesion. For the tumor response based on the tumor burden of a subset of lesions (injected/uninjected lesions) or individual lesions, a response is achieved if the percentage of tumor burden reduction from baseline is at least 50%. The related endpoints, such as time to response, may also be evaluated if appropriate.

Safety Endpoints:

- Subject incidence of treatment-emergent and treatment-related adverse events

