At each subsequent tumor assessment, the sum of the products of the two largest perpendicular diameters of the index lesions are added together to provide the total tumor burden.

Follow-up “Nonindex Lesions”:

Nonindex disease measurements are not required and these lesions should be followed as “present”, “absent”, or in rare cases “unequivocal progression”.

Follow-up “New Lesions”:

At tumor assessment, if new measurable lesions have appeared they should be added to sum of the products of the two largest perpendicular diameters of the index lesions to provide the total tumor burden. For nonmeasurable new lesion they should be followed as nonindex lesion as “present”, “absent”, or in rare cases “unequivocal progression”. If a new lesion(s) that appears in between scheduled tumor response assessments disappear(s) before the next scheduled assessment, there is no need to include this lesion for tumor response evaluation.

Response Criteria

Evaluation of Objective Response:

The subject response will be assessed based on the response of the index lesions and nonindex lesion, and presence or absence of new lesions. Confirmation of complete or partial response is not required. The overall response is derived from time point response assessments as described in [Table 1](#), [Table 2](#), and [Table 3](#).

Table 1. Definition of Index Lesion Tumor Response Including New Measurable Lesions

Complete Response (CR):	Complete disappearance of all index lesions, including any new measurable tumor lesions which might have appeared.
Partial Response (PR):	Achieving a 50% or greater reduction in the sum of the products of the two largest perpendicular diameters of all index lesions and new measurable lesions, if applicable, at the time of assessment as compared to the sum of the products of the perpendicular diameters of all index lesions at baseline.
Disease Progression (PD):	A > 25% increase in the sum of the products of the perpendicular diameters of all index tumors since baseline, or the unequivocal appearance of a new measurable lesion since the last response assessment time point.
Stable Disease (SD):	Neither sufficient tumor shrinkage of index lesion to qualify for response (PR or CR) nor sufficient tumor increase of index lesion to qualify for PD.
Unable to Evaluate (UE):	Any index lesion present at baseline which was not assessed or was unable to be evaluated leading to an inability to determine the status of that particular tumor for that time point.

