#### **4.1.2 Secondary Endpoint**

##### **4.1.2.1 Efficacy Endpoints**

##### **4.1.2.1.1 Tumor Response (Arm 1 Only)**

The overall tumor response is evaluated up to the earlier of surgical resection or subsequent anti-cancer therapy. Lesion-level response is evaluated up to the earliest event of start of subsequent anti-cancer therapy, merge with another lesion, or resection. Subject-level response is evaluated up to the earliest event of start of subsequent anti-cancer therapy or a partial or complete lesion resection.

Following endpoints will be analyzed for tumor response analysis,

- The overall tumor response is per the modified WHO criteria of tumor.
- Tumor response in injected/uninjected lesion(s)
  - The subject-level injected and uninjected responses will be based on the tumor burden of only injected index lesions including injected new measurable lesions, or the tumor burden of only uninjected index lesions including uninjected new measurable lesions, respectively.
  - The lesion-level injected and uninjected response will evaluate the change of the area of each individual lesion.
- Similar to tumor response in injected/uninjected lesions, lesion-level and subject-level response may also be conducted for lesion subtypes, eg, cutaneous / subcutaneous, nodal.

For the subject-level tumor response by tumor burden type (injected, uninjected lesions), a response is achieved if the percentage of the specific tumor burden type reduction from baseline for both baseline and new measurable lesions (if applicable) is at least 50%. Overall tumor burden is calculated at a visit as the sum of tumor areas of all lesions of the same type. The incidence of subject-level tumor response will be reported as the proportion of subjects with an evaluable tumor burden of the corresponding type that achieves a response.

The incidence of lesion-level response will be reported as the proportion of evaluable lesions in response. A lesion is in response if the decrease in tumor area is  $\geq 50\%$ .

All overall tumor burden and lesion response analyses will be based on bi-dimensional lesion measurements reported at a tumor assessment and will not consider injected lesion longest diameters reported at the time of investigational product administration forms.

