Pathological Complete Response (pCR) is defined as no evidence of viable tumor cells on complete pathological evaluation of the surgical specimen per institutional standards of care. pCR rate is defined as proportion of subjects which achieves a pCR. For each subject, the pCR status (pCR or non-pCR) will be determined based on whether or not viable tumor was detected in the surgical specimen.

- Last Valid Tumor Evaluation

For overall tumor response per modified WHO response criteria the last valid tumor evaluation refers to the last valid tumor response assessment (PR, CR, SD or PD) per investigator. For the subject-level tumor response based on the tumor burden of a subset of lesions (injected, uninjected lesions, or other subtype) or the lesion-level response the last valid tumor evaluation refers to the assessment where the corresponding tumor burden or the corresponding individual tumor area is not missing.

- Baseline Lesion

Lesions measured at the most recent visit on or before receiving the first administration of talimogene laherparepvec (i.e., study day 1) will be flagged as baseline lesions. Baseline lesions must have positive tumor area. Lesions reported in the baseline measurable lesion CRF page but with a tumor area of zero or missing value at the last measurement on or before study day 1 will not be considered baseline lesions.

- New Lesion

New lesions are those that first appear after study day 1 with a positive tumor area or lesions without a positive lesion area in the last assessment on or before study day 1

but a positive lesion area from follow up tumor measurements. Baseline tumor area of a new lesion is obtained from the earliest date with positive bi-dimensional tumor measurements after study day 1. If a new lesion(s) that appears in between scheduled tumor response assessments disappear(s) before the next scheduled assessment, there is no need to include this lesion for tumor response evaluation

- Evaluable Lesion

A baseline or new measurable lesion is defined as evaluable if it has an initial positive area followed by at least 1 assessment with a non-missing area.

- Injected/Uninjected Lesion

Baseline or new lesions that are reported as injected with talimogene laherparepvec at any time during the treatment period are considered injected lesions. Baseline or new lesions that are not reported as injected with talimogene laherparepvec are considered uninjected lesions.

- Baseline Tumor Burden

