The baseline tumor burden for a subject is the sum of the initial area of baseline lesions of the specific lesion type.

- Tumor Burden

The tumor burden for a subject at a visit is the sum of the area at that visit of baseline lesions of the specific lesion type.

- Evaluable Tumor Burden

A subject is defined as having an evaluable tumor burden of a specific type (injected, uninjected) if they have at least one evaluable tumor burden assessment of the specific type. An evaluable assessment is one with a tumor burden that includes all lesions of the specific type with a non-missing area that were included in a baseline tumor burden assessment.

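### SAP Section 6 defines visit-level tumor burden from baseline lesions only, contradicting SAP 4.1.2.1.1 and the protocol, which count new measurable lesions

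*SAP*

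**What the plan says.** Two rules for the same quantity stand in the SAP.

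- **SAP Section 6, Tumor Burden:** the burden at a visit is "the sum of the area at that visit of baseline lesions of the specific lesion type".
- **SAP Section 6, Baseline Tumor Burden:** "The baseline tumor burden for a subject is the sum of the initial area of baseline lesions of the specific lesion type".
- **SAP Section 6, New Lesion:** "New lesions are those that first appear after study day 1 with a positive tumor area". New lesions are therefore a separate class from baseline lesions.
- **SAP 4.1.2.1.1:** subject-level injected response rests on the "tumor burden of only injected index lesions including injected new measurable lesions", with a parallel rule for uninjected lesions. Response requires that the "reduction from baseline for both baseline and new measurable lesions (if applicable) is at least 50" percent. The section adds: "Overall tumor burden is calculated at a visit as the sum of tumor areas of all lesions of the same type".
- **Protocol 10.1.1.2:** the subject-level endpoint uses "injected index lesions including injected new measurable lesions", again with a parallel rule for uninjected lesions.
- **Protocol Appendix D, follow-up of new lesions:** "if new measurable lesions have appeared they should be added to sum of the products" for the index lesions, which gives the total burden.

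SAP Section 11, which lists departures from the protocol, does not mention tumor burden.

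**The concern.** The endpoint in SAP 4.1.2.1.1 is built on the term tumor burden, and Section 6 gives that term a narrower meaning. The same measurements can then produce two different sets of responders, and a programmer working from either section could claim to be following the SAP.

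New lesions are not a remote possibility here. Protocol 3.1 expects that new tumors may appear on treatment and lets such subjects continue to week 12. Protocol 2.2 reports that 54% of objective responders on talimogene laherparepvec in the earlier phase 3 study had interval progression first, a category that includes new lesions. The protocol schedules one tumor assessment between baseline and surgery (week 12, or shortly before earlier surgery), so a subject's classification rests largely on that visit.

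**Working it through.** The plan states no response rate or sample-size figure for this endpoint, so there is nothing to reproduce. The check is algebraic, followed by illustrations on assumed values.

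**Notation, for one subject and one lesion type**
- B = baseline burden, from baseline lesions only (Section 6, Baseline Tumor Burden; the partial-response rule in Appendix D Table 1 likewise compares with index lesions at baseline).
- V = area of those baseline lesions at the visit.
- W = area of new measurable lesions of the same type at the visit, W ≥ 0.

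**Reductions under the two rules**
- Section 6: R6 = 1 − V/B.
- SAP 4.1.2.1.1 and the protocol: R4 = 1 − (V + W)/B.
- Difference: R6 − R4 = W/B ≥ 0.

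Anyone with R4 ≥ 50% therefore also has R6 ≥ 50%, so among the same evaluable subjects Section 6 cannot give fewer responders. The two rules disagree exactly when V ≤ 0.5B and W > 0.5B − V.

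**Worked case (assumed values: B = 400 mm², V = 180 mm²)**
- R6 = 1 − 180/400 = 55%, a response whatever W is.
- Margin: 0.5 × 400 − 180 = 20 mm².
- W = 20: R4 = 1 − 200/400 = 50%, still a response.
- W = 60: R4 = 1 − 240/400 = 40%, no response.
- W = 100: R4 = 1 − 280/400 = 30%, no response.

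**Effect on a reported rate (assumed numbers)**

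Randomizing 150 subjects 1:1 puts 75 in Arm 1. Suppose all 75 are evaluable and 22 respond under 4.1.2.1.1. Intervals are exact 80% Clopper-Pearson, as SAP Table 2 specifies.

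| Subjects misclassified | Rate | 80% CI |
|---|---|---|
| 0 | 22/75 = 29.3% | 22.4 to 37.1 |
| 1 | 23/75 = 30.7% | 23.6 to 38.5 |
| 3 | 25/75 = 33.3% | 26.1 to 41.3 |
| 5 | 27/75 = 36.0% | 28.6 to 44.0 |

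Each misclassified subject adds 1/75 = 1.3 percentage points, or 1/60 = 1.7 points if only 60 are evaluable.

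**The case against.** The best reply is that the SAP already says which text governs. Section 6 opens by sending the reader to Section 4 for efficacy endpoint definitions, and its Response entry points to 4.1.2.1.1. That section states the inclusion of new lesions in three ways, and the protocol agrees. On this view the Tumor Burden entry is leftover glossary text. This stands as evidence of intent: 4.1.2.1.1 is the rule the authors meant. It does not remove the conflict, because 4.1.2.1.1 relies on a term that Section 6 then defines differently. Nor can the entry be read loosely. Where Section 6 means both classes, as in its Evaluable Lesion and Injected/Uninjected Lesion entries, it names both.

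A second reply is that the direction is not certain, since Section 6 gives each new lesion its own initial area. If that area entered the denominator, the sign could reverse: baseline lesions falling from 100 to 55 and a new lesion from 20 to 0 give 1 − 55/100 = 45% without the new lesion and 1 − 55/120 = 54% with it. The Baseline Tumor Burden entry and Appendix D both keep the denominator to baseline lesions, so the documents do not support that reading.

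Three stronger inferences should be resisted.
- **That the rate will be inflated.** It rises only if some subject's new area exceeds 0.5B − V. Otherwise it is unchanged.
- **That uninjected response suffers most.** Protocol 6.2.1.1 puts new injectable tumors first in the recommended injection order, and Section 6 classes a lesion injected at any time as injected. New lesions may well fall in the injected burden.
- **That the Evaluable Tumor Burden entry is also wrong.** It works as a completeness rule for baseline lesions and does not bar new lesions from the sum.

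**Conclusion.** The contradiction is real and should be corrected. Section 6 states a visit-level burden that differs from SAP 4.1.2.1.1 and from the protocol, with no declared change. With the baseline-only denominator, applying it can leave the subject-level response rate unchanged or raise it, but never lower it.

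The size in this trial cannot be determined, because neither the frequency nor the area of new measurable lesions is given. The figures above are illustrations.

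The reach is narrow: subject-level injected and uninjected response, and the optional lesion-subtype version, in Arm 1 only. These are secondary, descriptive results. Lesion-level response uses individual lesion areas. Overall response is taken from the investigator, and under Appendix D an unequivocal new measurable lesion counts as progression. RFS does not use tumor burden. A reader might infer that the sponsor plans a biased response analysis. The pointers to 4.1.2.1.1 argue against that, and the defect is better described as a wrong definition that could be programmed in good faith.

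**What to change.** Amend the Tumor Burden entry in SAP Section 6 so that the visit sum runs over baseline lesions and new measurable lesions of the specific type. Keep the Baseline Tumor Burden entry unchanged, so that the denominator stays baseline-only. The Evaluable Tumor Burden entry can stay as it is. Extending it to require non-missing new-lesion areas would be a separate decision, since it could make some subjects non-evaluable and change the denominator of the rate.

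The cost is an edit to one definition. No new data are needed, because Appendix D already requires new measurable lesions to be added to the burden. SAP 10.1 takes the primary analysis of neoadjuvant response from the second interim data, so any response program or output already produced should be checked for which definition it used.

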## **7. Analysis Subsets**

### **7.1 Intent to Treat Analysis Set**

The primary analysis of all efficacy endpoints of the study will be conducted on the intent to treat analysis set defined as all randomized subjects who were randomized to either treatment arm. All subjects will be analyzed according to their treatment randomization.

## 7.2 Safety Analysis Set

The safety analysis set will include all randomized subjects who received talimogene laherparepvec or surgical resection of melanoma tumor lesion(s). The safety analyses will be performed by treatment received (i.e., neoadjuvant talimogene laherparepvec + surgical resection versus surgical resection alone). Subjects will be classified in the talimogene laherparepvec arm for safety analyses if they received at least one administration of talimogene laherparepvec at any time during the treatment period.

## 7.3 Efficacy Analysis Set

The efficacy analysis set will include all subjects in Arm 1 who received at least one dose of talimogene laherparepvec and surgical resection of melanoma tumor lesion(s) and all the subjects in Arm 2 who received surgical resection of melanoma tumor lesion(s). In addition, all subjects in the efficacy analysis set must have achieved histopathologic tumor-free margin (R0) status after surgery and should not have any important protocol deviations considered to affect efficacy outcomes listed in [Section 10.3](#).

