#### 4. Study Endpoints and Covariates

##### 4.1 Study Endpoints

##### 4.1.1 Primary Endpoint

Recurrence-Free Survival (RFS): The event for RFS is defined as the first of local, regional, or distant recurrence of melanoma or death due to any cause. RFS is defined as time from randomization to the date of the event. The following **four** rules will be used:

1. For subjects having not experienced an event by the cutoff date, RFS will be censored at the last valid tumor evaluation (refer to Section 6 for the definition of last valid tumor evaluation).
2. Subjects who are not confirmed to be disease-free post-surgery (i.e., who do not have an R0 surgical outcome) will be considered to have an event at randomization for RFS.
3. Subjects who withdraw prior to surgery will be considered to have an event at randomization for RFS.
4. Subjects with a non-melanoma tumor or a second malignancy identified before or at surgery will be censored at the day after randomization.

Alternative RFS definitions will be evaluated in sensitivity analyses as follows.

- **RFS Sensitivity # 1: RFS is defined as the first of local, regional, or distant recurrence of melanoma or death due to any cause, regardless of surgical outcome, achieved by omitting rule 2.**

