### **9.4 Detection of Bias**

#### **9.4.1 Important Protocol Deviations (IPD) Impact**

All IPDs will be reported, documented, and stored in eClinical (Clinical Trial Management System). An IPD report will be produced using Cognos by the Clinical Study Manager for regularly scheduled Study Team IPD Review meetings and before each analysis.

Lack of protocol compliance and the potential for biased statistical analyses will be examined by tabulating subjects with important protocol violations by study arm. A

listing of all IPDs will also be provided. High rates of lack of compliance or differing rates between study arms could be an indication of bias. A sensitivity analysis will be performed on the primary efficacy endpoint for the impact of important protocol deviations by repetition of analysis using the **Efficacy Analysis Set** (see [Section 7.3](#)).

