## 10. Statistical Methods of Analysis

### 10.1 General Principles

All analyses will be descriptive with no formal hypothesis testing.

In principle, mean, standard deviation, median, first and third quartiles, minimum and maximum will be calculated for continuous variables; frequency and percent will be calculated for binary and categorical variables. Graphical summaries of the data may also be presented.

Analyses of tumor tissue or serum biomarkers may be performed after collection of all samples during the conduct of the study and therefore may be reported after the primary analysis of efficacy endpoint.

The primary analysis for efficacy endpoints will be performed on the Intent to Treat Analysis Set by randomized treatment. In addition, some of the analysis may be repeated on the Efficacy Analysis Set by treatment actually received. Safety analyses will be conducted on the Safety Analysis Set.

Data analysis is scheduled to occur at the following time points:

- Two interim analyses with no formal stopping rules will be performed when approximately 40 and 75 subjects randomized to talimogene laherparepvec have had the opportunity to complete the safety follow-up visit. (Please refer to [section 8.1](#) for details).
- An additional third interim analysis with no formal stopping rule is planned to evaluate RFS approximately 1 year after the end of randomization. This analysis will be conducted by the Amgen study team. (Please refer to [section 8.1](#) for details).
- The primary analyses for RFS will occur at the later time of either the occurrence of approximately 64 events (local, regional, or distant recurrence of melanoma or death) or approximately 2 years after end of randomization. The primary analysis for certain secondary endpoints (eg, response to neoadjuvant treatment, R0 resection rate, pCR rate, and safety) will be performed using the data from the second interim analysis.
- The final analyses will occur approximately 5 years after the end of randomization. An additional analysis will also occur approximately 3 years after the end of randomization.
- Ad hoc analyses for safety or some efficacy endpoints (eg, response to neoadjuvant treatment, R0 resection rate, pCR rate) may be conducted before the planned primary and/or final analyses if interim data are required for submission to regulatory authorities. These ad hoc analyses will be executed by the **Amgen study** team.

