## 10.3 Important Protocol Deviations

Important Protocol Deviations (IPDs) categories are defined by the study team before the first subject's visit and updated during the IPD reviews throughout the study prior to database lock. These definitions of IPD categories, deviation codes and descriptions will be used during the course of the study. The final IPD list is used to produce the summary of IPDs table and the list of subjects with IPDs by deviation category, subcategory, and randomized treatment. A separate summary table and listing will also be provided for inclusion/exclusion deviations.

Subjects with the IPDs considered affecting efficacy outcomes will be excluded from the Efficacy Analysis Set (see [Section 7.3](#)).

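### The planned check on protocol deviations (SAP 9.4.1) uses a set that also requires surgery and R0, so it cannot isolate the effect of deviations on RFS

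*SAP*

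**What the plan says.** SAP 9.4.1 states the purpose: "A sensitivity analysis will be performed on the primary efficacy endpoint for the impact of important protocol deviations by repetition of analysis" in the Efficacy Analysis Set. The same section examines deviations otherwise by "tabulating subjects with important protocol violations by study arm" and by a listing.

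SAP 7.3 sets several conditions for membership. Arm 1 subjects need at least one dose and surgery; Arm 2 subjects need surgery. In addition, "all subjects in the efficacy analysis set must have achieved histopathologic tumor-free margin (R0) status after surgery". Members must be free of efficacy-affecting deviations, and subjects not treated as assigned are left out. Protocol 10.1.2 has the same dose, surgery and R0 conditions, but offers the set only for sensitivity analysis in general, if needed.

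SAP 4.1.1 imputes RFS events in two situations. Rule 2 covers subjects "who do not have an R0 surgical outcome) will be considered to have an event at randomization for RFS". Rule 3 reads: "Subjects who withdraw prior to surgery will be considered to have an event at randomization for RFS".

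On which deviations count, SAP 7.3 refers to "important protocol deviations considered to affect efficacy outcomes listed in" Section 10.3. SAP 10.3 says "Subjects with the IPDs considered affecting efficacy outcomes will be excluded from the Efficacy Analysis Set" and refers back to 7.3. Section 7.3 itself names two eligibility deviations.

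**The concern.** A rule-2 subject fails the R0 condition and a rule-3 subject fails the surgery condition. All of these subjects, and their events, leave the analysis whether or not they deviated. With no deviations at all, a set that drops only deviators would equal ITT; this one does not.

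The selection is also related to treatment. R0 is a post-randomization outcome that Protocol 2.3 expects treatment to raise. Rule-3 removals may be uneven too: SAP 3.1 places surgery at weeks 13 to 18 in Arm 1 and at weeks 1 to 6 in Arm 2, which leaves Arm 1 longer to withdraw.

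At stake is how one sensitivity analysis is read. The repeat can move away from ITT with nobody deviating, or stay level with ITT while deviations matter. Either could be reported as evidence about deviations. No other planned RFS analysis drops deviators while keeping the rule-2 and rule-3 events.

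**Working it through.** **Inputs.** SAP 3.2 and Table 1: 150 subjects 1:1, 2-year RFS 0.70 v 0.60, exponential RFS, 10% exponential drop-out, 80% intervals. Protocol 3.5.1: 18-month accrual. R0, withdrawal and deviator rates are not in the documents and are assumed.

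**Plan's own figures.** For the first row of Table 1, HR = ln 0.70 / ln 0.60 = 0.698. With 64 events the 80% interval is 0.70 × exp(±1.2816 × 2/√64) = 0.51 to 0.96. The probability that it lies below 1 is Φ(|ln 0.70| × √64/2 − 1.2816) = Φ(0.145) = 0.56. All three agree with the table, so the design figures are not in question.

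**Identity.** Rule-2 and rule-3 subjects fail at time 0. If a share p of an arm is operated and R0, then RFS(ITT, 2y) = p × RFS(set, 2y). The events deleted are 75(1 − p1) + 75(1 − p2).

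**Calibration A: 0.70 v 0.60 is the ITT result, no deviations.** The set HR is ln S1 / ln S2.

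| R0, Arm 1 v Arm 2 | 2-year difference in set (ITT 0.100) | ITT HR → set HR | Events deleted |
|---|---|---|---|
| 90% v 90% | 0.778 − 0.667 = 0.111 | 0.69 → 0.2513/0.4055 = 0.62 | 15 |
| 95% v 90% | 0.737 − 0.667 = 0.070 | 0.71 → 0.3054/0.4055 = 0.75 | 11.25 |
| 90% v 80% | 0.778 − 0.750 = 0.028 | 0.71 → 0.2513/0.2877 = 0.87 | 22.5 |

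The ITT HRs are large-sample Cox values with Efron ties.

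For rule 3 alone, suppose 3 of 75 Arm 1 subjects withdraw before surgery, none in Arm 2, and every operated subject is R0. The difference becomes 0.70/0.96 − 0.60 = 0.129.

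**Calibration B: 0.70 v 0.60 holds among operated R0 subjects, no deviations.** The set HR is then 0.70 and the set difference 0.100.

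| R0, Arm 1 v Arm 2 | ITT 2-year difference | ITT HR → set HR |
|---|---|---|
| 95% v 95% | 0.665 − 0.570 = 0.095 | 0.73 → 0.70 |
| 90% v 90% | 0.630 − 0.540 = 0.090 | 0.75 → 0.70 |
| 90% v 80% | 0.630 − 0.480 = 0.150 | 0.63 → 0.70 |

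Both calibrations agree on direction. With equal R0 rates the imputed events dilute the ITT HR, and deleting them moves it away from 1. With more non-R0 subjects in Arm 2, deleting them moves it towards 1.

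**Trials of the planned size.** These simulations have 75 per arm, no deviations, follow-up uniform over 2 to 3.5 years and 10% drop-out. A shift means |ln(HR set / HR ITT)| > ln 1.1. Ranges cover both calibrations and repeat runs. The benchmark removes subjects at random at the same rates.

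| R0, Arm 1 v Arm 2 | Shift > 10%, set | Shift > 10%, random removal | Median HR ratio, set / ITT |
|---|---|---|---|
| 95% v 95% | 31–38% | 10–11% | 0.96 |
| 90% v 90% | 51–66% | 25–28% | 0.89–0.93 |
| 95% v 90% | 43–53% | 16–20% | 1.06–1.08 |
| 90% v 80% | 63–80% | 31–40% | 1.12–1.25 |

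Under random removal the median ratio is about 1.00.

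**No shift is not reassuring either.** This example is constructed. Let 10 of 75 Arm 1 subjects deviate, with 2-year RFS 0.40, and let the ITT result be 0.70 v 0.60. Dropping only the deviators gives (0.70 − (10/75) × 0.40)/(65/75) = 0.746, a difference of 14.6 points against 10.0 in ITT. If R0 is 97.3% among the remaining Arm 1 subjects and 90% in Arm 2, the set shows 0.746/0.973 − 0.60/0.90 = 10.0 points, level with ITT.

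**The case against.** The strongest reply is that this is a matter of labelling. The R0 condition comes from the protocol, SAP 7.3 describes the set's use only as a sensitivity analysis of the primary endpoint, the trial is descriptive, and ITT remains primary. That is right as far as it goes: the fault lies in the purpose that 9.4.1 assigns to the set. But relabelling alone would leave the plan with no estimate of deviation impact on RFS, which 9.4.1 undertakes to give.

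The plan also has safeguards. SAP 10.2 tabulates treated and untreated subjects and the reasons for no surgery, by randomized arm. SAP Table 2 gives ITT R0 rates by arm with their difference. RFS Sensitivity #1 drops rule 2. Together they show how much non-R0 and unoperated status contributes, and they make misreading less likely. None isolates deviations: Sensitivity #1, for example, excludes no deviators and keeps rule 3.

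Some stronger readings are tempting but not supported:

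- A reader might take the simulated shares as entirely due to the selection. The random-removal column shows that a good part is the noise of a smaller set.
- A reader might infer that the deviations are left undefined. SAP 10.3 has categories set before the first subject's visit, updated until database lock and fixed in a final list. Only the efficacy-affecting subset is left to a circular reference.
- A reader might see a conflict in SAP 10.1, where "some of the analysis may be repeated on the Efficacy Analysis Set by treatment actually received". That sentence concerns efficacy analyses in general, not RFS, and does not contradict the firm commitment in 7.3 and 9.4.1. The RFS row of Table 2, which makes the repeat conditional on need, does sit badly with them.

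**Conclusion.** The point holds on the text alone: followed exactly, the 9.4.1 analysis cannot answer the question it is set, because its result mixes deviations with the removal of every rule-2 and rule-3 event and with selection on R0. It should be changed, but it does not touch the ITT primary result.

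The systematic distortion is modest at R0 95% in both arms (median HR ratio 0.96). It is larger at 90% v 80% (1.12–1.25), and its direction depends on which arm has more imputed events. These sizes rest on assumed R0 rates, no deviations, exponential RFS and 75 per arm; the range reflects whether 0.70 v 0.60 is applied to R0 subjects or to ITT. The masking example shows only that masking is possible, not how likely it is.

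**What to change.** In SAP 9.4.1, base the deviation-impact analysis on the ITT set minus subjects with pre-listed efficacy-affecting important deviations, including the two eligibility deviations named in 7.3, with rules 2 and 3 kept. State that neither non-R0 status nor withdrawal before surgery is by itself a reason for exclusion. Apply the assigned-arm exclusion there only to subjects who received the other arm's treatment; otherwise an untreated withdrawal could be dropped under that heading. Label the result a sensitivity analysis, because removing post-randomization deviators is still a selection.

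Keep the R0-restricted Efficacy Analysis Set of Protocol 10.1.2 and SAP 7.3 as a separate supportive, non-randomized analysis, not described as a measure of deviation impact. Do not repeat the R0 rate in it, as Table 2 allows: it is 100% in both arms by construction.

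Two small repairs go with this. Resolve the 7.3/10.3 circular reference by flagging in the final deviation list which deviations affect efficacy. For RFS, reconcile the firm wording of 7.3 and 9.4.1 with the conditional wording in Table 2.

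The cost is SAP wording, one exclusion flag and one extra RFS repeat. The protocol-defined set is unchanged.
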